8.2 Secondary study parameter(s)

Analyses of the *preliminary effects* on the outlined immune parameters will be conducted using an intention-to-treat principle. The exercise intervention effect on markers of immune cell infiltration and activity will be evaluated using linear regression analyses in which the intervention is regressed on the post-test value of the marker, adjusting for the baseline value (ANCOVA). Additionally, we will explore whether the exercise effect on NK-cell infiltration is moderated by receptor expression of epinephrine and IL-6 on NK-cells with interaction tests. As this feasibility trial is underpowered by design, we will primarily explore the average size of the effect to identify whether it may have the potential to be clinically relevant, instead of observing statistical significance only ($p \leq 0.05$). Additionally, we will calculate the sample size required to detect the same difference in effect with 80% power (alpha 5%).

Preliminary effects of the intervention on physical fitness and QoL will be explored using linear (continuous outcomes), logistic (dichotomous outcomes) and cox (survival data) regression analyses. In the linear regression analyses, we will adjust for baseline values. We will use a multilevel model to take account for the clustering of patients within hospitals.

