6. METHODS

6.1 Study parameters/endpoints

6.1.1 Main study parameter/endpoint

Feasibility will be judged according to two key questions:

1) Recruitment

What is the proportion of eligible patients who are willing to participate in this study and undergo an additional tumor biopsy?

2) Quality of tumor material

What is the percentage of tumor biopsies that can be examined successfully both at baseline and after 6 weeks of neo-adjuvant treatment?

We define a biopsy as successful if we collected enough tumor tissue and the quality of the tissue enables us to perform IHC-analysis to determine the infiltration of NK-cells into the tumor.

We conclude that our feasibility-study is successful if:

1. we achieve a recruitment rate of at least 20%.
2. we can examine biopsies successfully on infiltration of NK-cells (both on T0 and T1) in 14 of 20 patients (70%).

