6.1.2 Secondary study parameters/endpoints

Preliminary treatment effects:

1. Changes in immune cell infiltration measured with tumor biopsy

Primary end-point for the preliminary effects is the alteration in number of NK-cells per total number of lymphocytes and in NK-phenotype.

Tumor tissue will be investigated by immunohistochemistry (IHC) to assess immune cell infiltration into the tumor with a specific focus on NK-cell frequency and phenotype.

Tumor tissue will be obtained with tumor biopsies. Tumor biopsies at diagnosis are performed as part of usual care. An additional tumor biopsy will be performed after 2 or 3 cycles of chemotherapy (6 weeks).

2. Immune function measured from blood.

Venous blood samples will be drawn prior to the start of chemotherapy and randomization (T0), and after 2 (3-weekly) or 3 (2-weekly) cycles of chemotherapy (T1). At T0 we will collect 20ml blood and at T1 we will collect 24ml blood to measure immune function. This 4ml extra blood on T1 is used to determine levels of leukocytes and thrombocytes prior to the biopsy. Immune cells will be investigated in whole blood using fluorescence activated cell sorting (FACS), to determine the frequency of CD4⁺ T cells, CD8⁺ T cells, regulatory T cells, B cells, monocytes, granulocytes, circulating dendritic cell (DC) subsets, myeloid derived suppressor cells, and the frequency, phenotype and function (i.e. cytotoxic potential, cytokine production capacity, and IL-6 and epinephrine receptor expression) of NK cells as demonstrated and reported previously [15].

3. IL-6 levels measured from blood

Patients included from the VUmc and randomized to the intervention group will be asked for consent to draw venous blood samples prior to and directly after one of the exercise sessions to examine acute responses to exercise. At both measurements we will collect 5ml blood. This will be done to measure Interleukine-6 levels (IL-6) which are supposed to be present in elevated concentrations during- and directly after exercise as outlined in the rationale for this study [16].

4. Physical fitness:

This will be assessed as secondary end-point to determine whether the exercise intervention yielded the expected physiological responses in 6 weeks.

- Aerobic fitness will be assessed during a submaximal endurance test performed on a cycle ergometer assessing the time that a patient can cycle at 70% of the estimated work load based on the steep ramp test, until a maximum of 30 min.[3]

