6.2 Randomisation, blinding and treatment allocation

After baseline assessment, patients will be randomized into the exercise or the control group by the use of a computerized random generator. Randomization is stratified for TNBC (yes/no), extent of disease (N+/N-) and treatment (regular versus dose-dense).

The researcher that examines the physical fitness will not be blinded to group allocation.

The pathologist and analyst that will examine the blood and biopsy tissue will be blinded to group allocation.

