7.2 AEs, SAEs and SUSARs

7.2.1 Adverse events (AEs)

Adverse events are defined as any undesirable experience occurring to a subject during the study, whether or not considered related to the experimental intervention. For this study, all exercise-related AE's and AE's related to the biopsy (T1) and blood sampling (T0 en T1) reported spontaneously by the subject or observed by the investigator or his staff will be recorded.

In case a subject (with 3-weekly AC chemotherapy cycles) receives a prescription for G-CSF (pegfilgrastim) prior to the second cycle of chemotherapy (in case of neutropenia) this

will be reported by the coordinating researcher, because this might interfere with the secondary outcomes on immune function.

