8. STATISTICAL ANALYSIS

8.1 Primary study parameter(s)

Information on trial feasibility and preliminary effects are crucial to set up a randomized controlled trial with sufficient statistical power to evaluate the exercise effects on immune cell infiltration into the tumor.

The *feasibility* will be assessed using the following descriptive statistics:

- The proportion of eligible patients who are willing to participate in this study and undergo an additional tumor biopsy.
- The percentage of tumor biopsies at baseline and after 6 weeks of neo-adjuvant treatment that can be assessed successfully.

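### Minor: the immune-marker ANCOVA in section 8.2 adjusts for the baseline value only, although randomisation is stratified by TNBC, nodal status and regimen; stating where those factors enter is a cheap improvement

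*Protocol*

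**What the plan says.** - **Allocation.** Protocol section 6.2: "Randomization is stratified for TNBC (yes/no), extent of disease (N+/N-) and treatment (regular versus dose-dense"). That is three binary factors, so 8 strata.
- **Immune model.** Section 8.2 analyses tumour and blood markers alike, by linear regression in which "the intervention is regressed on the post-test value of the marker, adjusting for the baseline value (ANCOVA"). No section places the stratification factors in any model.
- **Regimen and timing.** Section 6.1.2 puts the second sample "after 2 (3-weekly) or 3 (2-weekly) cycles of chemotherapy (T1"), so regimen sets how much chemotherapy precedes the outcome. Section 7.2.1 has G-CSF prescriptions in 3-weekly patients reported "because this might interfere with the secondary outcomes on immune function".
- **Which marker leads.** Section 6.1.2: "Primary end-point for the preliminary effects is the alteration in number of NK-cells per total number of lymphocytes and in NK-phenotype". Section 8.1 says the later trial is meant to "evaluate the exercise effects on immune cell infiltration into the tumor".
- **Use of the result.** Section 8.2 calls the trial underpowered by design, puts effect size ahead of significance, and adds: "Additionally, we will calculate the sample size required to detect the same difference in effect with 80% power (alpha 5"%).
- **Expected yield of biopsies.** The only figure is the success criterion in section 6.1.1: "we can examine biopsies successfully on infiltration of NK-cells (both on T0 and T1) in 14 of 20 patients (70"%).

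**The concern.** Stratified allocation makes the arms more alike on the chosen factors, so part of the chance variation in the treatment estimate is removed by design. A model without those factors does not know this. It leaves their contribution in the residual variance and reports a standard error that is larger than the true spread of the estimate. The protocol names its covariate, and the set it names omits the groups it randomised within. At least one of these, regimen, is tied by the protocol itself to the state of the patient at T1.

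What is at stake is precision and the description of variability. Section 8.2 treats the size of the effect as the finding and plans a sample-size calculation from it, so the interval and the residual SD are what a reader will use. If the later trial adjusts for its strata, the SD it needs is the adjusted one.

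**Working it through.** **Plan's own figure.** The protocol gives no SD, correlation or explained variance for any marker, so there is no precision figure to reproduce. The biopsy criterion is consistent: 14/20 = 70%.

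**Inputs from the protocol.** 20 patients (section 3); 14 paired biopsies as the success threshold (section 6.1.1); three binary factors (section 6.2); arm plus baseline as the model (section 8.2).

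**Assumptions, not in the protocol.** 1:1 allocation in permuted blocks of 2 or 4 within the 8 strata; factor prevalences 30%, 50% and 50%; random loss where fewer than 20 are evaluable; share of residual variance explained by the factors (R) of 0, 10 or 20%, spread evenly over the three factors unless stated.

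**Step 1: degrees of freedom.** df = n - 3 - q, with q extra terms.

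| Evaluable | Model | df | t (97.5%) |
|---|---|---|---|
| 20 | baseline only | 17 | 2.110 |
| 20 | plus three factors | 14 | 2.145 |
| 14 | baseline only | 11 | 2.201 |
| 14 | plus regimen | 10 | 2.228 |
| 14 | plus three factors | 8 | 2.306 |

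**Step 2: direction and upper bound of the error.** With perfect balance on the factors, reported SE / true SE = 1/√(1 - R). At R = 20% this is 1/√0.8 = 1.118. Balance is incomplete with 20/8 = 2.5 patients per stratum, so the realised excess is smaller: simulation gives a baseline-only SE 5-9% too large and coverage of 96-97%.

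**Step 3: simulated mean 95% CI half-width** (blocks of 2, in residual SDs given baseline).

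| Evaluable | Terms added | R | Baseline only | Adjusted | Change |
|---|---|---|---|---|---|
| 20 | three | 0 | 0.955 | 0.995 | +4% |
| 20 | three | 10% | 0.963 | 0.952 | -1% |
| 20 | three | 20% | 0.965 | 0.895 | -7% |
| 14 | three | 0 | 1.231 | 1.393 | +13% |
| 14 | three | 20% | 1.225 | 1.237 | +1% |
| 14 | regimen | 0 | 1.223 | 1.268 | +4% |
| 14 | regimen | 20%, spread evenly | 1.225 | 1.223 | none |
| 14 | regimen | 20%, all from regimen | 1.232 | 1.138 | -8% |

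Over blocks of 2 and 4, the 20-patient changes are +4 to +6% at R = 0, about nil at 10% and -6 to -7% at 20%.

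**Step 4: where the gain comes from.** At 20 patients and R = 20% the empirical SD of the estimate is 0.436 without the factors and 0.434 with them, while type I error moves from 0.038 to 0.051. The estimate itself is hardly more precise; the reported SE becomes the right size.

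**Step 5: the pilot's own uncertainty.** The 95% CI for a residual variance is df/χ² times the estimate: 0.56 to 2.25 at 17 df and 0.50 to 2.88 at 11 df. Leaving out factors with R = 20% inflates the residual variance by 1/0.8 = 1.25, well inside either range.

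**The case against.** The strongest case against is that stratifying without adjusting is a valid analysis, that extra covariates are commonly left to a SAP, and that the trial calls itself underpowered. Much of this stands. Nothing in sections 6.2 and 8.2 is logically inconsistent, and a SAP that is not shown may already add the factors. What remains is that section 8.2 is not silent: it states a model and names one covariate.

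It can also be said that the lead marker is the biopsy marker, for which the primary model proposed here is the protocol's own. That is true, and it limits the point to blood markers plus one sensitivity analysis.

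The G-CSF passage is weak support. It concerns individual prescriptions after baseline, which a regimen term does not remove. The firmer ground for regimen is the 2 versus 3 cycles before T1. Nothing in the protocol shows TNBC or nodal status to be less prognostic for infiltration, so preferring regimen is a judgement.

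Four stronger readings are tempting but not supported:
- **That the planned analysis is biased or anti-conservative.** Baseline-only type I error was never clearly above 5% in any setting, and mean bias was at most 0.01 SD.
- **That adjustment is sure to help the blood markers.** This depends on an explained share that the protocol does not give. The method of stratifying is not stated either; if allocation were effectively simple, break-even at 20 patients would move to about 20%.
- **That three factors can never be justified for biopsy markers.** Fourteen is the success threshold, not the expected yield. With 20 evaluable pairs the degrees of freedom equal those for blood, and even at 14 pairs all three factors narrow the interval at R = 30% (1.235 to 1.165 under blocks of 2).
- **That the next trial would be sized wrongly.** The protocol supplies no SD or effect, and the sampling error in step 5 exceeds the effect of the omission.

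**Conclusion.** The point holds as a minor one. Section 8.2 states a model that leaves out the groups within which section 6.2 randomises, one of which also sets the number of cycles before the outcome is measured. If the factors are prognostic, the baseline-only interval is modestly too wide: at 20% of residual variance explained, the SE is 5-9% too large with 20 evaluable patients. If they explain less than about 10%, adjustment brings no gain or a small loss. Estimates, type I error control and both feasibility criteria are unaffected.

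The direction follows from the design alone. The sizes rest on the assumed blocking, factor prevalences and explained share, so they should be read as a range. Confidence is medium.

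**What to change.** Replace the covariate statement for immune markers in section 8.2 (or settle it in the SAP before unblinding) with:

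> Blood immune-marker models will adjust for the baseline value and, as main effects, TNBC, nodal status and regimen. For biopsy markers the baseline-only model is primary, and a model adding regimen is a sensitivity analysis. The residual SD of both models will be given beside the sample-size calculation.

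Regimen is chosen for the biopsy sensitivity model because it is the factor best supported by the protocol when only about 14 pairs are evaluable.

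Cost: wording only. TNM classification, receptor status and treatment are already collected (section 6.1.3). The blood model gives up 3 degrees of freedom. If the factors are uninformative, its CI is about 4-6% wider with 20 evaluable patients and 7-9% wider with 17; with 17 it is still 2-3% wider at 10% explained and 3-5% narrower at 20%. The biopsy sensitivity model costs 1 degree of freedom and about 4% in CI width if regimen is uninformative; the primary biopsy analysis does not change.

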3. STUDY DESIGN

This is a multicenter randomized controlled feasibility trial, in which 20 women with breast cancer scheduled for neoadjuvant 2 or 3 weekly AC-T(H) chemotherapy will be randomized into a combined aerobic and resistance exercise intervention group or a usual care (no exercise)

control group, during the first 6 weeks (2 or 3 cycles) of chemotherapy. Patients from the control group will receive care as usual and are requested to maintain their usual daily physical activities. In order to limit contamination (increase of exercise in the control group), non-participation and prevent dropout, the control group will be offered the same 6-week exercise intervention after the tumor biopsy has been taken after 6 weeks. The study design and timepoints of measurements are presented in Figure 2.

[figure not shown]

Figure 2. Study design and time-point of measurements

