4.4 Sample size calculation

Eligible patients will be recruited from Amsterdam UMC and 2 other sites. In these hospitals, over 100 patients receive neoadjuvant chemotherapy with Adriamycin/Cyclofosfamide treatment for breast cancer every year. With an anticipated accrual rate of 37% (corresponding to our previous REACT [14] and METRIC (NTR 4105) trials) recruitment will be completed after 7 months. In case accrual rates drop to 25%, patient enrollment will be completed after 10 months.

This study is a pilot trial focusing on evaluating study feasibility and preliminary effects of exercise on immune function. For the preliminary effects, the feasibility trial is underpowered by design. We will primarily explore the average size of the effect to identify whether it may have the potential to be clinically relevant, instead of observing statistical significance only ($p \leq 0.05$). Additionally, we will calculate the sample size required to detect the same difference in effect with 80% power (alpha 5%).

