- Physical activity will be assessed by the Short Questionnaire to Assess Health-enhancing physical activity (SQUASH). The SQUASH contains 11 items and measures the frequency, duration and intensity of 4 different physical activities (actively commuting, physical activity at work or school, household activities and leisure time activities).
- Health-related Quality of Life (HRQoL) will be assessed by the European Organization Research and Treatment of Cancer Quality of Life Questionnaire (EORTC QLQ) Core on baseline and after the intervention (T1).
- A questionnaire on demographic and clinical covariates will be assessed on baseline. This questionnaire includes questions about smoking, alcohol, exercise history and sociodemographic characteristics (e.g. age, ethnicity, education level, living situation).

Clinical data

Clinical data will be obtained from medical records on baseline, during and/or after the intervention. This includes information on extent of the tumor, disease, treatment and treatment-related toxicity, hospitalization, performance status (ECOG), comorbidities and co-medication.

Exercise logs

To collect data on adherence and compliance to the exercise, physical therapists will be asked to register data in exercise logs. These exercise logs will be collected at T1 by the researcher.

If this pilot-trial determines feasibility, we will strive to set up a sufficiently powered RCT. In that case, data collected in this pilot trial might be used as part of the data collection of this next RCT. Patients will be asked for consent to use the coded data (not the human material) for this next RCT.

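### The follow-on trial's sample size is to be calculated from the effect seen in this 20-patient pilot, so its 80% power is not assured and mean true power falls short

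*Protocol*

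**What the plan says.** Section 3 of the protocol states that "20 women with breast cancer scheduled for neoadjuvant 2 or 3 weekly AC-T(H) chemotherapy will be randomized" to exercise or usual care. Section 6.1.1 counts the biopsy criterion as met if T0 and T1 samples can both be examined "in 14 of 20 patients (70"%). Section 6.5 does not replace drop-outs.

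For the immune markers, section 8.2 specifies a linear regression in which "the intervention is regressed on the post-test value of the marker, adjusting for the baseline value (ANCOVA"). It accepts that the pilot lacks power for these effects and says "we will primarily explore the average size of the effect to identify whether it may have the potential to be clinically relevant". It then adds that "we will calculate the sample size required to detect the same difference in effect with 80% power (alpha 5"%). Section 4.4 has the same sentence.

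Two other places show what the calculation is for. Section 8.1 opens with "Information on trial feasibility and preliminary effects are crucial to set up a randomized controlled trial with sufficient statistical power". Section 6.3 says "If this pilot-trial determines feasibility, we will strive to set up a sufficiently powered RCT".

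**The concern.** In both sections the sentence follows directly on the pilot's average effect. The natural reading is that the next trial's size will be calculated for the difference observed here. The protocol names no other planning effect, no external SD and no allowance for imprecision.

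A power formula treats the effect put into it as the truth. Required size varies with the inverse square of that effect. An estimate that is too high by chance gives a trial that is far too small, and one near zero gives an impossibly large trial. Low estimates do not compensate for high ones, because power cannot exceed 100% but can fall a long way below 80%.

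At stake is the later randomised trial. If it is too small, its patients would undergo a research-only biopsy in a study unlikely to answer the question.

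**Working it through.** **Inputs from the protocol.** 20 patients randomised (section 3); 14 of 20 paired biopsies as the success line, 14/20 = 70% (section 6.1.1); 80% power and alpha 5% (sections 4.4 and 8.2). The protocol gives no effect size, SD or follow-on sample size, so there is no stated number to reproduce.

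**Assumptions.** 1:1 allocation; the 14 pairs split evenly, so 7 to 10 per arm; two-sided test; true effects of 0.3, 0.5 and 0.8 SD.

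**Step 1: precision of the pilot effect.** SE = √(2/n) SD, which is 0.53 SD with 7 per arm and 0.45 SD with 10. The 95% half-width is t(0.975; 2n−2) × √(2/n):
- 7 per arm: 2.179 × 0.535 = 1.16 SD
- 10 per arm: 2.101 × 0.447 = 0.94 SD

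**Step 2: one worked case.** Size per arm ≈ 2(1.96 + 0.84)²/d² = 15.7/d². For a true d = 0.5 this is 63 (64 with the t correction). If the pilot estimate is one SE too high:
- 7 per arm: d = 0.5 + 0.53 = 1.03, giving 15 per arm; true power 28%.
- 10 per arm: d = 0.5 + 0.45 = 0.95, giving 18 per arm; true power 32%.

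**Step 3: all outcomes.** 200,000 pilots were simulated per setting. Each observed standardised effect (absolute value, none discarded) gave a size per arm, and the power of that size was then evaluated at the true effect. Results are for 7 / 10 per arm, without baseline adjustment:

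| True effect | Mean true power | Share of sizes reaching 80% |
|---|---|---|
| 0.3 SD | 55% / 60% | 36% / 41% |
| 0.5 SD | 66% / 69% | 46% / 48% |
| 0.8 SD | 71% / 73% | 49% / 50% |

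At a true 0.5 SD, the 10th to 90th percentile of the calculated size is 11–1392 / 14–1396 per arm. The observed effect has the wrong sign in 17% / 13% of pilots, and 37% / 33% of the calculated sizes give under 50% power. Repeat runs agree to within one or two points for the powers and shares. The upper percentiles of size move a little more, because they come from estimates near zero.

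**Step 4: does the planned ANCOVA rescue it?** With an assumed T0–T1 correlation of 0.5 and sizing on the residual SD, mean power at the three effects is 58–63%, 68–70% and 72–74%. Over correlations of 0 to 0.7 it is 54–66%, 65–72% and 71–75%. The shortfall remains.

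**Step 5: does screening out poor estimates rescue it?** At a true 0.5 SD, mean power is 61–65% if only positive estimates go forward. It is 52–56% if they must also need at most 200 per arm (an assumed cap). Selection makes it worse, because the estimates that survive are more often too high.

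**The case against.** The strongest case against is about weight. This is a feasibility study, and neither its success criteria nor its conduct depends on the calculation. No section binds a later trial to the calculated number, and that trial would need its own protocol and justification. The plan already admits low power, looks first at clinical relevance and adds the calculation as a supplement. Intervals or sensitivity ranges might appear in an analysis plan that is not shown. All this bears on how serious the point is. It does not change the fact that the protocol commits twice to one sizing method, offers no other, and in section 8.1 ties the later trial's power to these effects.

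A second objection is that the shortfall is one of mean power. That is right and should be said. Median power is about 73–78% at 0.5 SD and close to 80% at 0.8 SD, and at 1.0–1.2 SD the mean shortfall is only about 4 to 7 points. But section 1 says it is unknown whether the mechanism operates in human tumours, so a large effect cannot be presumed. Even at 0.8 SD, about half of the calculated sizes miss 80%.

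A third is that sizes near 1,400 would be screened out in practice. Probably so, but step 5 shows that screening lowers mean power further.

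Finally, a fixed target does not guarantee power either. With a 0.5 SD target and a true effect of 0.3 SD, mean power is 51–54%, slightly below the 55–60% of the protocol's method. This stands, and it is a reason to prefer a grid of differences.

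**Conclusion.** The concern holds and should be fixed. Sizing on the pilot's own difference does not assure 80% power, and mean true power is below 80% in every setting examined: about 54–75% for true effects of 0.3 to 0.8 SD when all pilots are carried forward, with or without baseline adjustment. The calculated size is also too unstable to plan with.

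The conclusion rests on reading the protocol's planning difference as the one observed in this pilot. The figures rest on 1:1 allocation, 7 to 10 evaluable patients per arm, a two-sided test and the assumed true effects. Seven per arm is a success threshold and not a floor, so precision could be worse; blood markers may have more evaluable patients than biopsies. That the later trial would use the number is an inference from section 8.1.

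**What to change.** In sections 4.4 and 8.2, replace the sentence with wording such as:

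*The sample size for a subsequent RCT (80% power, two-sided alpha 5%) will be calculated for a pre-stated smallest worthwhile difference in the NK-cell endpoint on its own scale, or for a small grid of such differences. From the pilot we will use only the ANCOVA residual SD, at its upper one-sided 80% confidence limit, and will report the T0–T1 correlation it reflects. The pilot effect will be reported with its 95% CI and will not be used as the planning effect.*

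The grid is the practical choice, since the effect in human tumours is unknown. The SD multiplier is √(df / 20th percentile of chi-square): 1.25 with 14 evaluable patients (11 df) and 1.19 with 20 (17 df). The 80% limit is a convention, and another stated limit would serve.

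With a 0.5 SD target, mean power is 88% if the truth is 0.5 SD, 73–75% if it is 0.4 and 51–54% if it is 0.3. The calculated size has a 10th to 90th percentile range of 52–156 per arm (7 per arm in the pilot) or 54–131 (10 per arm), against 11 or 14 to about 1,400 under the current wording.

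The cost is new wording in two sections, with no extra patients or data in this trial. The later trial may come out larger, and its power holds only if the pre-stated difference is true.

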4. STUDY POPULATION

4.1 Population (base)

Eligible patients will be recruited from Amsterdam UMC and 2 other sites.

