6.3 Study procedures

After providing informed consent (IC), patients will be randomized in either the intervention or waitlist control group.

Participants in the intervention group will attend supervised exercise sessions twice a week at a local physical therapist and are encouraged to be physically active for at least 30 minutes per day at Borg level 12-14 (see paragraph 5.1).

Participants in the control group are requested to maintain their usual daily physical activities and are offered supervised exercise sessions after 6 weeks at the expense of the study budget (see paragraph 5.1).

Study parameters will be assessed at baseline (before start of chemotherapy) and after 6 weeks of chemotherapy (2 3-weekly or 3 2-weekly cycles) in the patient's own treating hospital. When patients are included from the Amstelland hospital they will be asked beforehand to come to the Amsterdam UMC – location VUmc for the physical test, blood samples and biopsy. Consequently, Amstelland will be a recruiting hospital in this study.

During the visits, information on physical fitness and blood samples will be collected. In addition, during the visit on T1 a tumor biopsy will be obtained. The T1 biopsy and physical fitness test will not be performed on the same day, as this might lead to contamination of the results on immunoreactivity in blood and tumor. We will strive to perform the physical fitness tests prior to the 3th (3-weekly) or 4th (2-weekly) chemotherapy administration so patients don't have to come to the hospital an extra time.

The visit on T0 will last approximately 75 minutes, the first visit on T1 (biopsy and blood sample) approximately 30 minutes and the second visit on T1 (physical fitness test) approximately 45 min.

Questionnaires will be sent to the participant's home and will take up to 10 minutes to complete, based on 6 items per minute. Questionnaires will be sent in paper only. Table 1 presents a summary of all study parameters.

	Measurement tool	-1	T0	T1
Primary outcome measurement				
Recruitment		X		
Quality of tumor material	Tumor biopsy		X	X
Secondary outcome measurement				
Clinical data				
Extent of the tumor	Medical records		X	
Disease, treatment and toxicity	Medical records		X	X
Performance status	Medical records		X	X
Co-morbidities and co-medication	Medical records		X	
Physical tests				
Aerobic fitness	Steep ramp test & endurance test		X	X
Muscle strength	1 RM legpress and 1 RM bench press		X	X
BMI	Height		X	
	Weight		X	X

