6.5 Replacement of individual subjects after withdrawal

In case of drop-outs, patients will not be replaced by including extra patients because feasibility of patient enrollment is one of the primary outcomes of this study. This also includes patients with an infection at T1 and thereby an exclusion for the biopsy.

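### The multilevel model for hospital clustering in section 8.2 cannot be usefully fitted with three sites and 20 patients, and gives slightly narrow intervals for the fitness and QoL effects

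*Protocol*

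**What the plan says.** Section 8.2 has two paragraphs. The first covers the immune markers and specifies linear regression of the post-test value on arm and baseline (ANCOVA), with no mention of hospital. The second covers fitness and quality of life. It lists linear, logistic and Cox regression, adds "In the linear regression analyses, we will adjust for baseline values", and closes with "We will use a multilevel model to take account for the clustering of patients within hospitals".

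The design facts that bear on this sentence are:

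- Sites (section 4.1): "Eligible patients will be recruited from Amsterdam UMC and 2 other sites".
- Sample size (section 3): a trial "in which 20 women with breast cancer scheduled for neoadjuvant 2 or 3 weekly AC-T(H) chemotherapy will be randomized".
- Drop-outs (section 6.5): "In case of drop-outs, patients will not be replaced by including extra patients". The analysed number can therefore only fall below 20.
- Randomisation (section 6.2): individual patients, and hospital is not a stratum: "Randomization is stratified for TNBC (yes/no), extent of disease (N+/N-) and treatment (regular versus dose-dense".
- Measurement (section 6.3): patients from one site are tested at another: "Consequently, Amstelland will be a recruiting hospital in this study".

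The protocol gives no ICC, estimation method, degrees-of-freedom method or fallback for this model.

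**The concern.** A random hospital effect is useful when there are enough hospitals to learn how much they differ. With three, the model has almost nothing to learn from. It will often report no hospital variation at all, and otherwise a value with very wide uncertainty, which the interval for the arm effect then treats as known.

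At stake are the intervals around the fitness and quality-of-life effects. Section 6.1.2 uses fitness to judge whether six weeks of the programme produced the expected physiological response. Section 8.2 puts effect size ahead of significance (for the immune markers, in so many words), so an honest interval matters more than a p-value. Because patients are randomised individually, there is also a simpler analysis that is valid and loses little.

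**Working it through.** **The plan's own figures.** None is given for the multilevel model. The only computed figure tied to N=20 is recruitment time in section 4.4, and it reproduces. At 37% accrual of 100 patients a year, 20 / (100 × 0.37 / 12) = 6.5 months (stated 7). At 25%, 20 / (100 × 0.25 / 12) = 9.6 months (stated 10).

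**Step 1: information on the hospital variance.** Three hospitals give J − 1 = 2 degrees of freedom. Suppose each hospital mean were known without error. The 95% interval for the variance is then the estimate times 2/χ²(0.975; 2) to 2/χ²(0.025; 2), that is 2/7.378 = 0.27 to 2/0.0506 = 39.5. That is the best case.

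**Step 2: simulation.** Inputs from the protocol: N=20, three hospitals, individual randomisation not stratified by hospital, linear model with arm and baseline, alpha 5%. Assumptions not in the protocol: 1:1 allocation, two-sided 95% intervals, hospital sizes 7/7/6 or 12/5/3, baseline correlation 0.5, ICC 0 to 0.20. There were 3,000 null trials per row, so the Monte Carlo error is about √(0.93 × 0.07 / 3000) = 0.5 points. Critical values are z = 1.96, t(17) = 2.11 and t(15) = 2.13. Coverage in %:

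| Sizes | ICC | REML variance = 0 | Multilevel, z | Multilevel, t(17) | No hospital term, z | No hospital term, t(17) | Fixed hospital, t(15) |
|---|---|---|---|---|---|---|---|
| 7/7/6 | 0 | 61% | 91.7 | 93.8 | 92.7 | 94.4 | 94.0 |
| 7/7/6 | 0.05 | 52% | 92.8 | 94.6 | 93.3 | 95.3 | 95.4 |
| 7/7/6 | 0.10 | 44% | 92.6 | 94.5 | 93.5 | 95.4 | 94.9 |
| 7/7/6 | 0.20 | 33% | 91.1 | 93.4 | 92.7 | 94.4 | 94.5 |
| 12/5/3 | 0 | 63% | 93.0 | 94.7 | 93.3 | 95.3 | 95.4 |
| 12/5/3 | 0.05 | 55% | 92.1 | 94.4 | 93.2 | 95.1 | 94.5 |
| 12/5/3 | 0.10 | 50% | 92.7 | 94.9 | 93.5 | 95.3 | 95.4 |
| 12/5/3 | 0.20 | 37% | 91.9 | 93.8 | 92.9 | 94.5 | 94.8 |
| Mean | | | 92.2 | 94.3 | 93.1 | 95.0 | 94.9 |

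A separate run over the same ICC range gave zero variance in 32–64% of trials. Coverage there was 91.9–93.0% (multilevel, z), 93.4–94.9% (multilevel, t), 92.6–94.0% (no hospital term, z) and 94.4–95.6% (fixed hospital, t). At ICC 0.05 the mean REML variance in the table's runs was 1.95 and 2.26 times the true value, so the estimate is unreliable upwards as well. Maximum likelihood with z is worse than REML, at 89.6–91.0%.

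**Step 3: where the shortfall comes from.** From the row of means, the gap between ANCOVA with t and the multilevel model with z is 95.0 − 92.2 = 2.8 points. Of this, 95.0 − 93.1 = 1.9 arise from using z instead of t, with no hospital term in the model. The remaining 93.1 − 92.2 = 0.9 arise from the random hospital effect. With t throughout, the random effect costs 95.0 − 94.3 = 0.7 points.

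**Step 4: price of a fixed hospital factor.** For 7/7/6 at ICC 0, the standard deviation of the arm estimate is 0.432 with fixed hospital and 0.404 without a hospital term. Relative interval width is about (0.432/0.404) × (2.13/2.11) = 1.08. At ICC 0.20 it is (0.432/0.434) × (2.13/2.11) = 1.00.

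**The case against.** The strongest reply is that the sentence does little harm. When the hospital variance is estimated as zero, the result is ordinary ANCOVA, which is valid here because randomisation is individual. Section 8.2 does not prescribe z intervals. Software and the degrees-of-freedom method are normally settled in a statistical analysis plan, and the same model with a t reference is close to nominal. The outcomes are exploratory, and the protocol says openly that the trial lacks power for effects.

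Much of this stands. A reader might infer that having few hospitals is what makes the intervals too narrow. Step 3 does not support that: about two thirds of the shortfall under z is present with no hospital term at all. A reader might also take the variance to be impossible to estimate. Software will return a number; the number is not useful.

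Three further extensions are not supported:

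- **Fewer patients.** Under-coverage is larger with 14 patients, but that number is the biopsy success threshold in section 6.1.1. Nothing in the protocol ties it to fitness or quality of life.
- **Logistic and Cox models.** It is tempting to call multilevel versions unworkable. They were not simulated, and the sentence directly follows one about linear models, so its reach is open to reading.
- **Other endpoints.** The feasibility criteria are descriptive, and the immune-marker paragraph specifies plain ANCOVA. Neither depends on this sentence.

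The reply does not rescue the choice of model. That choice is written into the protocol rather than left open. Even with a t reference it covers slightly less well than the simpler analyses, and in many trials it makes no hospital adjustment at all.

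**Conclusion.** The point holds at low severity. The protocol commits the fitness and quality-of-life analyses to a model that three sites and 20 patients cannot support. The hospital variance is estimated as zero in about one third to two thirds of trials. Coverage is about 92–93% with z and about 93.5–95% with t on n-3 degrees of freedom, against about 95% for ANCOVA with a t interval, with or without a fixed hospital factor.

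These sizes rest on the assumed ICC range, baseline correlation and hospital sizes, and on software defaults that the protocol does not name. Counting the locations of Amsterdam UMC separately (four clusters), or grouping Amstelland patients with the place where they are measured (possibly two), does not change the conclusion. No success criterion in section 6.1.1 uses the affected intervals.

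**What to change.** In section 8.2, replace the multilevel sentence with: *In the linear models recruiting hospital enters as a fixed factor and 95% confidence intervals use the t distribution; logistic and Cox models, if used, carry no hospital term.*

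Naming the recruiting hospital settles the ambiguity created by patients who are recruited at one site and tested at another. Omitting hospital from the linear models and using t intervals would also hold about 95% coverage. The fixed factor is suggested because it keeps the protocol's intention to account for hospital.

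The cost is one sentence and 2 degrees of freedom. Intervals are about 8% wider than ANCOVA without a hospital term if hospitals do not differ, and about equal by ICC 0.20.
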